#### 4.2.4. Study RP103-05

The objective of this study was to compare the rate and extent of absorption of two different modes of administration of cysteamine bitartrate delayed-release capsules (RP103) following a single dose of 600 mg administered under fasted conditions. The two modes of administration were: 1) intact delayed-release capsules and 2) content of opened delayed-release capsules.

Concentration data for 19 of 20 subjects who received active drug was included in the BE analysis in Periods 1 and 2. One subject was excluded from the study following Period 1 and 1 subject was excluded just prior to Period 3 due to an AE.

The rate and extent of absorption, as measured by  $AUC$ ,  $C_{max}$ , and  $T_{max}$ , was similar

for both the opened and intact capsule treatments when administered under fasted conditions. All estimates of the ratios for the parameters AUC(0-t), AUC(0-inf), and Cmax were near 1.00, and the 94.12% confidence intervals for all comparisons were within the acceptance range for bioequivalence of 0.80 - 1.25, and there were no significant sequence or period effects observed.

#### Parallel-Group Meal Delay Period 3

The number of subjects in each of the 4 meal delay treatment groups ranged from 3 to 5 subjects each. A decreased rate and extent of absorption was observed for both the opened and intact capsule treatments when a meal was administered 30 minutes following drug administration compared to fasted conditions. There appeared to be no difference in AUC or Cmax between the 2 hour meal, compared with fasted conditions for the opened capsules treatment and for the intact capsules treatment.

No statistically significant treatment differences were found among the 4 meal delay treatment groups, however, this finding may be attributed to the small sample sizes of the meal delay groups.

#### Safety Results

There were a total of 19 AEs reported during the crossover BE portion of the study (Periods 1 and 2). One subject in each treatment group was withdrawn from the study due to an AE prior to Period 3.

The most frequently reported AEs in the crossover BE portion of the study were in the gastrointestinal (GI) disorders SOC. Gastrointestinal disorders were reported in 5 of 20 subjects (25.0%) in the opened capsule group and 3 of 19 subjects (15.8%) in the intact capsule group. The GI events were primarily single episodes of nausea and abdominal pain. One subject reported a short episode of diarrhea at approximately 64 hours following dosing in Period 1, and no subjects vomited. Seventeen out of 19 AEs in the crossover BE portion of the study were considered possibly or probably related to the study drug by the Investigator.

The most frequently reported AEs in the meal delay portion of the study were in the gastrointestinal (GI) disorders SOC. Gastrointestinal disorders were reported in 9 of 17 (52.9%) of the subjects in the meal delay portion of the study and were observed more frequently in subjects who consumed their meal 2 hours after dosing than in subjects in the 30 minute meal groups. Three of 4 subjects (75.0%) in the opened capsule/2 hour meal delay group (AM2) experienced GI AEs and 4 of 5 subjects (80.0%) in the intact capsule/2 hour meal delay group (BM2) experienced GI AEs. One subject each in the 30 minute meal delay groups experienced GI AEs. Four subjects (23.5%) vomited during the meal delay portion of the study, and 3 of the 4 subjects experienced vomiting following the 2-hour meal delay. One subject experienced severe stomach ache, headache and shakiness, and another experienced severe nausea. Treatment with ondansetron, loperamide and IV fluids were given for multiple events of vomiting or diarrhea in 2 subjects. The majority of the events began between 2 and 4 hours after dosing. Thirty-five out of 36 AEs in the crossover BE portion of the study were

considered possibly or probably related to the study drug by the Investigator.

There were no significant changes in clinical safety laboratory results, vital signs or ECGs.

#### 4.2.5. Study RP103-06

Study RP103-06 was designed to demonstrate bioequivalence (BE) between oral administration of intact RP103 capsules with orange juice, and contents of opened capsules mixed with applesauce, taken orally. This was a single-center, open-label, randomized, 2 period, 2 sequence, crossover BE study. The design is identical to the previous BE study (RP103-05) with one exception: Treatment A (intact capsules) was administered with acidic juice, while Treatment B (capsule contents) was again sprinkled in a small amount of applesauce.

The outcome of Study RP103-06 was the same as for the previous BE Study RP103-05: The rate and extent of absorption, as measured by AUC, Cmax and Tmax, were similar for the intact and opened capsule treatments when administered under fasted conditions.

#### 4.2.6. Study RP103-HLTA-009

### 4.3. Risk/Benefits

Cystagon® (cysteamine bitartrate) is a cystine-depleting agent that is the only cystinosis treatment approved by FDA. Cystagon® is indicated for the management of nephropathic cystinosis in children and adults. Cystagon® is contraindicated in patients who have developed hypersensitivity to it or to cysteamine or penicillamine (Cystagon® Package Insert, 2007).

The most common adverse events (> 5%) associated with cysteamine were vomiting 35%, anorexia 31%, fever 22%, diarrhea 16%, lethargy 11%, and rash 7% (Cystagon® Package Insert, 2007). Less common adverse events associated with cysteamine include: CNS symptoms such as seizures, dizziness, lethargy, somnolence, depression, and encephalopathy; gastrointestinal tract symptoms including nausea, vomiting, anorexia and abdominal pain, sometimes severe. In addition, gastrointestinal ulceration and bleeding have been reported in patients on cysteamine therapy. Cysteamine has occasionally been associated with reversible leucopenia, abnormal liver function studies, skin lesions, headache, tinnitus, diplopia, blurry vision, loss of vision, pain behind the eye or pain with eye movement (Cystagon® Package Insert, 2007).

Patient adherence with Cystagon® is challenging due to significant adverse effects, dosing frequency, and the need for life-long treatment from the age of diagnosis. Since Cystagon® must be taken Q6H around the clock; patients must be awakened in the middle of the night to take their medication in order to maintain adequate white blood

cell cystine levels. One recent study demonstrated that only about 25% (5 of 22) of patients were actually adhering to with the Q6H regimen (Levtchenko, van Dael et al. 2006). A Q6H dosing schedule must be maintained for the rest of the patient's life, therefore preventing patients and / or their caregivers from obtaining a full night's sleep. Many of these patients are in their formative years where sleep plays a major role in patient well-being and overall health. A change from Q6H to Q12H is not merely for patient convenience, as the Q6H dosing must be adhered to for an entire lifetime, there is evidence that failure to adhere to this strict Q6H dosing regimen results in rapid deterioration of kidney function (Kleta, Bernardini et al. 2004). Thus, improved patient adherence will ultimately delay the time to kidney failure or the morbidity and mortality associated with renal replacement therapy such as dialysis or transplant, and hence greatly improves both the patient's quality and quantity of life.

Patients successfully completing the RP103-03 Study will be offered the opportunity to participate in this Study (i.e., Study RP103-04).

#### **4.4. Dose Rationale**

According to results obtained from Study RP103-01, it was predicted that RP103 should be administered twice a day, where the total daily RP103 dose is 70% of the patient's total daily Cystagon® dose (see Section 4.2). Furthermore, in the RP103-01 study, a dose of RP103 up to 167% of the entry level total daily Cystagon® dose has been studied and RP103 has been found to be safe and well-tolerated.

Patients completing RP103-03 and entering this Study will have received a stable dose of either RP103 or Cystagon® prior to Screening. Patients will continue to receive their Q12H RP103 dose as determined in the phase III Study (RP103-03). Patients that did not complete the RP103-03 study but qualify for the study based on the inclusion and exclusion criteria, may be enrolled after completion of the analysis of the RP103-03 Study where the non-inferior efficacious and safe dose of RP103 versus Cystagon® has been determined. Patients that did not complete the RP103-03 study must be receiving a stable dose of Cystagon® prior to study entry and will have a starting Q12H RP103 dose at a total daily dose which is 70% of their total daily stable Cystagon® dose, administered twice a day.

If a subject does not achieve a meaningful reduction of WBC cystine level i.e., < 1 nmol ½ cystine/mg protein (see below for a discussion of this limit) or does not tolerate the dose, as determined by the Investigator, the subject may have their RP103 dose adjusted or may be terminated from the Study.

#### **4.5. Study Rationale**

Accurate measurements of intracellular cystine content are mandatory for the diagnosis and for the monitoring of the effects of cysteamine treatment. There are two components to the measurement, that for cystine content, and that for indexing the cystine content to the protein level of the cells in which it is measured.

Several methods have been developed to measure cystine content in leucocytes. They differ according to the type of cells used. Historically, cystine has been measured in mixed leucocyte preparations, despite the fact that it accumulates preferentially in polymorphonuclear granulocytes (PMNC).

Normal subjects have PMNC cystine levels lower than 0.25 nmol  $\frac{1}{2}$  cystine/mg protein. The diagnosis of cystinosis is confirmed when the PMNC cystine levels are  $> 2$  nmol  $\frac{1}{2}$  cystine/mg protein.

Cystinosis is treated specifically using cysteamine to reduce intracellular cystine levels. Following early publications (Thoene, Oshima et al. 1976), it was thought that the PMNC cystine level should be maintained lower than 2 nmol  $\frac{1}{2}$  cystine/mg protein for the treatment of cystinosis with cysteamine to be effective. For patients treated with Cystagon®, leukocyte cystine measurements are useful to determine appropriate dosage and drug adherence. "When measured 5 to 6 hours after Cystagon® administration, the goal should be a level  $< 1$  nmol  $\frac{1}{2}$  cystine/mg protein. In some patients with poorer tolerability for Cystagon®, patients may still receive benefit with a white blood cell cystine level of less than 2 nmol  $\frac{1}{2}$  cystine/mg protein" (Cystagon® Package Insert, 2007).

Variability exists in the measured cystine content in cells. Some of the variability arises from the types of cells harvested for the measurement. An even greater source of variation of the cystine level stems from the method used to determine the amount of protein used to normalize the result of the cystine assay with respect to total amount of protein in the cells. Although there is no explicit reference in the Cystagon® Package Insert as to which protein assay should be used to determine that the cystine level is less than 1 nmol  $\frac{1}{2}$  cystine/mg protein, the first laboratories known for measuring WBC cystine, have used the Lowry assay, which makes the Lowry assay as the method of reference, by default. The methods for the analysis of cystine and cellular total protein in white blood cells (WBC) for the current study were validated at [REDACTED] West Lafayette, IN under GLP principles (*good laboratory practice* or GLP specifically refers to a quality system of management controls for research laboratories and organizations to try to ensure the uniformity, consistency, reliability, reproducibility, quality, and integrity of chemical safety and efficacy tests). For that reason, [REDACTED] uses what is presently considered as the gold-standard assay to determine the amount of protein, the bicinchoninic acid assay (BCA) total protein method instead of the Lowry method. BCA is also used by some of the cystine determination laboratories that analyze patient samples in the US and Europe because, in addition to its being considered a more accurate assay for protein measurement, BCA is also better suited to implementing with rapid turnaround times and method robustness in a GLP compliant way than Lowry. However, during the conduct of this study, it was observed that the reported concentrations for cystine in WBC lysate from patient samples analyzed at [REDACTED] appeared to be consistently higher than the historical data that had been obtained previously from these patients at the cystine determination laboratories at academic medical centres that perform these assays, while on Cystagon. To address

to this concern, a series of analytic experiments was initiated to determine if the GLP methods validated at [REDACTED] were generating results equivalent to those previously reported under the Lowry method (Powell KL, Langman CB, Pediatr Nephrol 2012).

Based on these experiments, it was determined that the Lowry vs. BCA protein results had to be adjusted as follows:

$$\text{protein amount[Lowry]} = \text{protein amount[BCA]} * 1.6999 - 0.0648$$

The correction factor ensures the patients participating in the study to receive a safe and appropriate dose of RP103 in an effort to get their WBC cystine levels similar to levels reported historically (prior to their enrollment in Raptor's clinical studies). This also allows WBC cystine results reported from the clinical studies to be consistent with all previous clinical trials and surveys, as well as with previous Cystagon® guidelines.

Regular Q6H daily treatment with Cystagon® has been shown to diminish the rate of renal dysfunction as well as promoting improved growth in children with cystinosis (Kleta, Bernardini et al. 2004). Current guidelines for following WBC cystine levels are based on obtaining blood 5 to 6 hours after the last dose of Cystagon® (Schneider 2004). White blood cell (WBC) cystine content rapidly decreases after Cystagon® ingestion, but can return to predose levels within 6 hours (Smolin, Clark et al. 1988).

RP103 dose will then be increased by approximately 10% on regular time intervals until the WBC cystine level is < 1 nmol ½ cystine/mg protein or until the patient experiences some tolerability issue.

#### **4.6. Study Conduct**

This Study will be conducted in compliance with the protocol and any amendments approved by the local Institutional Review Boards (IRBs) or Ethics Committees (ECs), and according to FDA and ICH E6 Guideline for Good Clinical Practice. The Investigator must adhere to the protocol as detailed in this document and agree that the Sponsor must approve any change(s) to the protocol prior to seeking approval from the IRB or EC.

#### **4.7. Study Population**

Patients (male or female) with nephropathic cystinosis that successfully completed Study RP103-03 will be eligible for enrollment. Additional patients with cystinosis that did not complete the RP103-03 study but qualify for the study based on the inclusion and exclusion criteria, may be enrolled after completion of the analysis of the RP103-03 Study where the non-inferior efficacious and safe dose of RP103 versus Cystagon® has been determined.

## 5. Study Objectives and Endpoints

### 5.1. Study Objectives

The objective of this Study is to assess the long-term safety, tolerability, pharmacokinetics and pharmacodynamics of RP103 in pediatric and adult patients with cystinosis.

#### 5.1.1. Primary Objective

- To assess safety and tolerability of long-term repeat dosing of RP103 in patients with cystinosis.

#### 5.1.2. Secondary Objectives

- To assess the steady-state pharmacokinetics (PK) and pharmacodynamics (PD) of RP103.
- [REDACTED]

### 5.2. Study Endpoints

#### 5.2.1. Safety Endpoints

The safety profile of RP103 will be investigated by safety reviews conducted by the Investigator at or prior to each Monthly or Quarterly visit and through adverse event report monitoring (including attribution of treatment-emergent adverse events and serious adverse events [SAEs]), physical examination (including basic neurological and skin assessment findings), vital signs, ECG and clinical laboratory testing as outlined in the Schedule of Events (Appendix 14.1).

#### 5.2.2. Pharmacokinetic Endpoints

The trough plasma cysteamine concentration will be measured from samples collected 0.5 hour post dose at each study visit.

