#### Pharmacokinetic/Pharmacodynamic Relationship

An examination of the individual plots of cysteamine plasma concentrations versus time and WBC cystine levels versus time indicated little or no delay between the maximum plasma cysteamine concentration and the minimum WBC cystine level for the majority of individuals. This would be indicative of minimal hysteresis (note that due to the few number of WBC cystine measurement timepoints rigorous conclusions cannot be drawn). Thus, the plasma concentration can be directly related to WBC cystine response as presented in **Figure 3** for RP103 and Cystagon®. Furthermore, there appeared to be no difference in the cysteamine plasma concentration versus WBC cystine response between RP103 and Cystagon®. The two sets of data were, therefore, combined for the subsequent modeling to an inhibitory effect sigmoid Emax model. Using this model, it was estimated that the maximum decrease in WBC cystine would

be to 0.058 nmol  $\frac{1}{2}$  cystine/mg protein starting from an initial value of 2.015 nmol  $\frac{1}{2}$  cystine/mg protein with an EC50 of 2.57 nmol/L cysteamine (Table 1). The gamma function was close to unity at 0.921. A plot of the predicted values from the model parameters with the observed values is presented in Figure 3.

**Table 1: Pharmacodynamic parameters using an inhibitory effect sigmoid Emax model for pooled data of WBC cystine response when cysteamine was administered orally as Cystagon® and RP103 to patients**

[figure not shown]
Parameter	Units	Estimate	SE	CV
Starting WBC cystine level	nmol $\frac{1}{2}$ cystine/mg protein 	2.015	0.303	15.06
EC 50	nmol/L	2.567	0.983	38.27
Final WBC cystine level	nmol $\frac{1}{2}$ cystine/mg protein 	0.058	0.217	376.9
Gamma	NA	0.921	0.362	39.36

 Using Lowry method to determine the amount of protein used to normalize the results in mg of protein ([name] – personal communication)

 Ibid

 Ibid

 Ibid

**Figure 3: Predicted cystine response to oral cysteamine compared to observed response using pooled data from patients receiving Cystagon® and RP103 with an inhibitory effect sigmoid  $E_{max}$  model**

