The pharmacokinetic (PK) parameters could not be accurately estimated following Stage 1 due to low blood concentrations of cysteamine. There appeared to be a lag time for absorption of intact capsules, as the majority of subjects did not have detectable levels of cysteamine until 6 hours after dosing, whereas more than half the subjects had detectable concentrations of cysteamine within 1 hour of dosing in the opened capsules treatment. Overall, approximately 40% of the plasma cysteamine concentrations between 0.5 and 12 hours were below the limit of quantitation for the opened capsules treatment and 72% were below the limit of quantitation for the intact capsules treatment. Therefore, the study was stopped after Stage 1 and the protocol was amended to include Stage 3. For Stage 3, four subjects already enrolled in Stage 1 were retested following the same procedures for intact capsules, but under fasted conditions. Stage 3 was conducted at the same clinical site as Stage 1, and the same protocol requirements and procedures were followed. A comparison of PK parameters obtained in the subset (n=4) of subjects who received the intact capsules treatment in fed and fasted states showed more rapid drug absorption under fasted conditions (median  $T_{max}$  of 3.25 hours versus 6.0 hours for fasted versus fed treatment). Mean  $C_{max}$  was approximately 1.8-fold higher and mean  $AUC$  was 1.6-fold higher for fasted as compared to fed subjects. Half-life was approximately 2.30 hours for both treatments. The study was stopped following Stage 3.

There were no deaths or severe adverse events reported in subjects who received single doses of RP103. No subjects were withdrawn from the study due to adverse events.

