#### 5.2.3. Pharmacodynamic Endpoints

The WBC cystine content will be measured from samples collected 0.5 hour post dose at each study visit.

[REDACTED]

[REDACTED]  
[REDACTED]  
[REDACTED]

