#### 6.1.1. Study Visits

For patients who completed Study RP103-03, study visits consist of:

- Screening Visit: The RP103-04 Screening visit occurs simultaneously with the RP103-03 Period 2 Day 7 (End of Study) visit. These patients will continue RP103 Q12H treatment at the last dose level prescribed during their participation in Study RP103-03.
- Monthly Study Visits are only for patients who completed Study RP103-03 and will begin within 1 month ( $\pm$  7 days) after study entry. Each patient will complete a minimum of 6 consecutive Monthly visits.
- Quarterly Study Visits will commence for each patient  $\geq$  1 month and  $<$  4 months after the patient has completed at least 6 consecutive Monthly visits. Each Quarterly visit will take place by the middle of the first month ( $\pm$  7 days) of each calendar quarter (i.e., January 15, April 15, July 15 and October 15).
- End of Study (EOS) Visit will be conducted within 7 ( $\pm$  2 days) from the last completed study visit or from the date of decision to terminate.

For patients who did not complete Study RP103-03, study visits consist of:

- Screening Visit which may occur up to 28 days prior to Day 1.
- Dose Confirmation Period (Days 1-5) which includes 3 study visits over 5 days.
  - Day 1 includes a morning study visit while the patient is fasted, with pre-dose blood samples collected for trough cysteamine and peak WBC cystine determination while the subject is still taking Cystagon®. RP103 treatment regimen begins at the clinic on the morning of Day 1, administered Q12H at a starting total daily RP103 dose equal to 70% of the Screening total daily Cystagon® dose. Patients will leave the clinic for Days 2-3 and take RP103 as instructed.

- Days 4 and 5 each include a morning study visit; RP103 Q12H treatment regimen continues.
- Quarterly Study Visits will commence for each patient by the middle of the first month ( $\pm$  7 days) of each calendar quarter (i.e., January 15, April 15, July 15 and October 15).
- End of Study (EOS) Visit will be conducted within 7 ( $\pm$  2 days) from the last completed study visit or from the date of decision to terminate.

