- Measure vital signs (blood pressure, heart rate, respiratory rate, and oral body temperature, see Section 9.11) within 30 minutes prior to RP103 administration.
- Obtain clinical laboratory tests (serum chemistry, hematology, and urinalysis, see Section 9.7) prior to RP103 administration.
- Obtain a 12-lead ECG (see Section 9.9).
- Subjects should be fasting for at least 2 hours prior to RP103 dosing.
- A meal or snack will be ingested between 30 and 60 minutes after RP103 dosing.
- Administer Q12H RP103 dose with an acceptable food or liquid as described in Appendix 14.9.
- Collect a cysteamine PK sample 0.5 hour (30 minutes) post RP103 dose administration. Actual collection time will be recorded.
- Collect a WBC cystine PD sample 0.5 hour (30 minutes) post RP103 dose administration. Actual collection time will be recorded.
- [REDACTED]
- [REDACTED]
- Dispense RP103 for home administration.
- Dispense new diary.
- Record concomitant medications.
- Monitor AEs.
- Schedule return clinic visit.

Perform a safety and PK/PD review prior to or at the study visit. If a patient does not achieve a meaningful reduction of WBC cystine level (i.e., < 1 nmol  $\frac{1}{2}$  cystine/mg protein) or does not tolerate the dose, as determined by the Investigator, the patient may have their RP103 dose adjusted or may be terminated from the Study.

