### 2.5.2. Pharmacokinetic Endpoints

The trough plasma cysteamine concentration is measured from samples collected 0.5 hour post dose at each study visit.

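### The PK endpoint is called trough but is sampled 0.5 h after an RP103 dose, and the SAP's PK/PD summaries do not separate these samples from pre-dose samples taken on Cystagon

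*Protocol*

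**What the plan says.** The protocol synopsis (Study Endpoints) and section 5.2.2 give the PK endpoint as: "The trough plasma cysteamine concentration will be measured from samples collected 0.5 hour post dose at each study visit". SAP 2.5.2 carries it over: "The trough plasma cysteamine concentration is measured from samples collected 0.5 hour post dose at each study visit". The PD endpoint in protocol 5.2.3 has the same timing: "The WBC cystine content will be measured from samples collected 0.5 hour post dose at each study visit".

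For patients who did not complete RP103-03, protocol 6.1.1 describes Day 1, while they are still on Cystagon, as having "pre-dose blood samples collected for trough cysteamine and peak WBC cystine determination". Footnotes p and q of the Schedule of Events (14.1) put their Screening samples at 5 to 6 hours after the last Cystagon dose and their Day 1 samples within 15 minutes before the first RP103 dose. At End of Study (9.1.6), patients still on RP103 are sampled 0.5 h after a dose, and patients back on Cystagon just before their next one.

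On the goal, protocol 4.5 says: "Current guidelines for following WBC cystine levels are based on obtaining blood 5 to 6 hours after the last dose of Cystagon". Sections 4.4, 8.5, 9.1.4 and 9.1.5 apply the figure of below 1 nmol ½ cystine/mg protein in the investigator's review on RP103.

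SAP 8.1 and 8.2 summarise WBC cystine and plasma cysteamine over time, by analysis visit and collected visit, overall and by subpopulation. SAP 8.1 also splits WBC cystine by baseline category. Figure 1 plots mean WBC cystine by collected visit. Nothing visible splits the values by sampling time or by drug.

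**The concern.** A trough is the level at the end of a dosing interval, just before the next dose. A sample drawn after a supervised new dose equals it only if nothing has yet been absorbed. No visible text argues that this is so for RP103 at 0.5 h. A reader of the study report would therefore take a post-dose concentration for a trough.

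The second problem is comparability. Where pre-RP103 values are end-of-interval on Cystagon and on-study values are 0.5 h post-dose on RP103, a difference between them mixes a change of drug with a change of sampling time. The same holds within the End of Study visit. PK and PD are a stated secondary objective (protocol 5.1.2), so what these summaries can claim matters. The third problem is that the WBC cystine goal was set for one point in the interval and is read at another.

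**Working it through.** The documents give no figure to reproduce. The check sets the passages side by side and then asks whether they settle the direction of any difference.

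**1. The samples as specified**

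| Sample | Drug | Timing | Called trough? |
|---|---|---|---|
| Screening, RP103-03 non-completers | Cystagon | 5 to 6 h after dose | No |
| Day 1, non-completers | Cystagon | within 15 min before first RP103 dose | Yes (cysteamine), with WBC cystine called peak |
| Days 4 and 5, Monthly, Quarterly | RP103 | 0.5 h after dose | Yes, in the endpoint definition |
| End of Study, still on RP103 | RP103 | 0.5 h after dose | Yes, in the endpoint definition |
| End of Study, back on Cystagon | Cystagon | just before next dose | No |

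One word covers both a pre-dose and a post-dose sample. Protocol 4.2.2 also reports the peak WBC cystine of RP103-03 after 12 hours on RP103, which is the end of its interval.

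**2. Baseline.** SAP 4.2.1 takes the last non-missing value before the first dose. For non-completers that is an end-of-interval Cystagon value. For completers it may come from the RP103-03 End of Study visit, whose PK/PD sampling time is not stated, so the mismatch is documented for non-completers only.

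**3. How unlike values can share a cell.** SAP 4.2.9 assigns every assessment to a month by date and keeps the one closest to the scheduled day. Take a Quarterly visit on Study Day 173 and an End of Study visit on Day 173 + 7 = 180, as an example. Both lie in Month 6 (after Day 165, up to Day 195), and the rule keeps Day 180. If that patient has returned to Cystagon, a pre-dose Cystagon value enters a cell of 0.5 h RP103 values. SAP 9.1 subtracts Cystagon days from exposure; the visible text of 8.1 and 8.2 has no such rule.

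**4. Direction.** Protocol Table 1 gives the model

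WBC = 0.058 + (2.015 − 0.058) / (1 + (C/2.567)^0.921).

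From RP103-01 (protocol 4.2.1) come the 12 h level of 2.89 µmol/L, Cmax 33.06 µmol/L, Tmax 2.78 h and half-life 5.85 h. Assumptions: EC50 read in µmol/L (it is printed in nmol/L), no PK-PD delay, a straight-line rise to Cmax, and decay until absorption starts.

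- At 12 h: C = 2.89, WBC = 0.98.
- At 0.5 h, absorption starting at once: C = 2.89 + (33.06 − 2.89) × 0.5/2.78 = 8.32, WBC = 0.55, which is 0.43 lower.
- At 0.5 h, absorption not yet started: C = 2.89 × exp(−0.693 × 0.5/5.85) = 2.72, WBC = 1.01, which is 0.03 higher.

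The sign turns on the absorption lag, which the documents do not give for fasted patients. With EC50 in nmol/L as printed, the model gives about 0.06 in each case and timing would not matter, but that does not fit the 0.62 observed in RP103-03. These values show only that the direction is open. They do not estimate a bias.

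**The case against.** The strongest reply is that this is mostly a matter of wording. RP103 is a delayed-release product with a late Tmax (2.78 h in RP103-01, 187 min in RP103-03), so at 0.5 h little may have been absorbed. The synopsis (Efficacy Assessments) already describes the measure as 0.5 h post-dose, and actual collection times are recorded. SAP 8.1 and 8.2 are descriptive, and their visible text plans no change from baseline. A true trough may be obtained elsewhere: protocol 11.1 plans profiles with Cmin, and 9.8 mentions an optional 12-hour PK substudy. Some nearby text is redacted, so a rationale for 0.5 h may exist. All of this stands, and it limits the point to labelling and comparability. It does not remove the conflict between label and definition, or the pooling of unlike samples.

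Two stronger readings are tempting.

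- *On-study control looks better than it is.* A reader might infer this from RP103-02, where "more than half the subjects had detectable concentrations of cysteamine within 1 hour of dosing in the opened capsules treatment", together with "little or no delay between the maximum plasma cysteamine concentration and the minimum WBC cystine level" in RP103-01. But RP103-02 dosed healthy volunteers fed, its PK parameters could not be accurately estimated, and detectable within 1 hour says nothing about the amount at 0.5 h. Most subjects on intact capsules had no detectable drug until 6 hours. The protocol itself warns that few WBC cystine timepoints were available in RP103-01.
- *Young children are affected more, so comparisons between subpopulations are confounded.* No passage says that children aged 6 or under open capsules more often. Study visits require a 2-hour fast, and the fasted studies RP103-05 and RP103-06 found similar rate and extent of absorption for opened and intact capsules. Those results do not give the 0.5 h level, but they weaken the inference.

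**Conclusion.** The point holds as a defect of labelling and comparability. On the face of both documents, the endpoint called trough is not one as the protocol uses the word. For RP103-03 non-completers, and for End of Study samples after return to Cystagon, the planned summaries put values from different drugs and different points in the interval side by side without distinction. The goal of below 1 nmol is likewise tied to a different point in the interval from the one sampled.

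The numerical effect is undetermined: the 0.5 h reading may lie below, at or slightly above the end-of-interval value. No formal test and no primary safety result depends on it. The conclusion assumes that the redacted text contains neither a justification of 0.5 h as a surrogate nor a rule that separates the samples. If it does, the remaining change is one of wording.

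**What to change.** 1. In the protocol synopsis, protocol 5.2.2 and SAP 2.5.2, replace trough with 0.5 h post-dose, or keep the word and justify it with data showing that the 0.5 h value stands in for the end-of-interval value.
2. In SAP 8.1, 8.2 and Figure 1, show the Cystagon samples (non-completers' Screening and Day 1, and End of Study after return to Cystagon) separately from the 0.5 h post-dose RP103 samples. State that the difference is not a like-for-like change. Note that the sampling time of the completers' baseline is to be documented.
3. Add a sensitivity summary of the RP103 samples by actual collection time relative to the dose. The visit procedures record the draw time; confirm that the clinic dose time is captured too.
4. Reconcile the passages that set the 0.5 h sampling time with those that give the timing behind the WBC cystine goal.

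The cost is wording, a little more tabulation and a less favourable endpoint label. No sample or visit changes. Moving the draw to before the dose is not proposed here: it would break a series that has already run through three interim study reports (SAP 4.3) for an unquantified gain, and the timing also feeds dose review.
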